7.3.7. Final effectiveness evaluation

Record the final effectiveness after all cycle of BESPONSA® is finished.

Check 'conducted' if final effectiveness is evaluated then record the date of evaluation. Check 'not conducted' if final effectiveness is not evaluated then select one reason why it is not conducted among 'death', 'follow up loss', or 'other'. If 'other', record the specific reason.

- Response criteria: Select one among 'CR', 'CRI', 'refractory disease', 'progressive disease', or 'Relapsed disease'.
- Plan for HCT: Check 'yes' if HCT is on plan or on ongoing for a subject.

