7.7. Data analysis

Analysis will be performed for safety group and effectiveness group.

- Safety group: Subjects who have been administered BESPONSA® at least once and evaluated with safety-related endpoints at least once.
- Effectiveness group: Subjects who have been evaluated based upon effectiveness endpoints as described in this protocol.

Detailed methodology for summary and statistical analyses of data collected in this study will be documented in a Statistical Analysis Plan (SAP), which will be dated, filed and maintained by the sponsor. The SAP may modify the plans outlined in the protocol; any major modifications of primary endpoint definitions or their analyses would be reflected in a protocol amendment.

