5.2 EFFECTIVENESS ANALYSIS SET

The effectiveness analysis set includes patients who have been administered BESONSA® at least once and evaluated based upon effectiveness endpoints.

Patients meeting any of the following criteria will be excluded in the effectiveness analysis set.

1. Patients who are not included in safety analysis set
2. Patients who do not have any response evaluation

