8.2.3 Effectiveness Analyses

The effectiveness analyses will be performed for Effectiveness analysis set.

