8.2.3.2 Last effectiveness

In order to identify last effectiveness of BESPONSA®, the 'effectiveness' is judged as follows based on the final effectiveness evaluation or the last cycle response evaluation(if the final evaluation is missing) and summarized by the number of subjects(n), percentage(%) and 95% confidence interval of percentage.

- Effective: CR, CRI
- Ineffective: Refractory disease, Progressive disease, Relapsed disease

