8.2.3.5 Effectiveness(Best overall response)

In order to identify effectiveness (best overall response) of BESPONSA®, the 'effectiveness' is judged as follows based on the best overall response during evaluation and summarized by the number of subjects(n), percentage(%) and 95% confidence interval of percentage.

- Effective: CR, CRI
- Ineffective: Refractory disease, Progressive disease, Relapsed disease

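### Both overall CR/CRi rates are rates among evaluated patients only; add the rate on the full safety analysis set, so that early deaths stay in the denominator

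*SAP*

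**What the plan says.** SAP 5.2 admits to the effectiveness analysis set patients who were "administered BESONSA® at least once and evaluated based upon effectiveness endpoints". It then excludes anyone outside the safety analysis set and, as its second exclusion, "Patients who do not have any response evaluation". Protocol 7.7 defines its effectiveness group in the same spirit: "Subjects who have been evaluated based upon effectiveness endpoints as described in this protocol".

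SAP 8.2.3 makes this the denominator throughout: "The effectiveness analyses will be performed for Effectiveness analysis set". Two overall CR/CRi rates are to be given with a 95% confidence interval:

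- **Last effectiveness (SAP 8.2.3.2, Table 32)** is judged "based on the final effectiveness evaluation or the last cycle response evaluation(if the final evaluation is missing") and is "summarized by the number of subjects(n), percentage(%) and 95% confidence interval of percentage".
- **Best overall response (SAP 8.2.3.5, Table 36)** is judged "based on the best overall response during evaluation and summarized by the number of subjects(n), percentage(%) and 95% confidence interval of percentage".

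In both, the ineffective category holds only refractory, progressive and relapsed disease. It has no place for a patient who was never assessed.

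Protocol 7.3.6 lets the response evaluation be marked as not done at any cycle, without a reason. For the final evaluation, protocol 7.3.7 does ask for one: "if final effectiveness is not evaluated then select one reason why it is not conducted among" death, loss to follow-up or other. SAP 7 imputes no missing response, drops missing values from the analysis concerned, and promises to evaluate the impact of missing data where appropriate, without naming an analysis.

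**The concern.** SAP 4 states the aim as real-life safety and effectiveness. A reader will take a CR/CRi percentage from such a study as the share of treated patients who responded. As planned, it is the share of those who lived and stayed under observation long enough to be assessed at least once.

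Being unevaluated is unlikely to be unrelated to outcome. Death is one of the listed reasons for a missing final evaluation, and protocol 5 puts median survival in relapsed or refractory adult disease at about 3-6 months. A patient who dies before any assessment belongs with the treatment failures, but is counted neither as effective nor as ineffective.

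The factor analyses in SAP 8.2.3.3 and 8.2.3.6 use the same selected set. A baseline factor that leads to early death could therefore look neutral for response, because the patients who show its effect have been removed.

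**Working it through.** There is no planned figure to reproduce. The documents state no expected response rate and no expected number unevaluated, and the basis for the 100 subjects is redacted.

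**Inputs**

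- N = patients in the safety analysis set. Set at 100 for illustration, the planned number (protocol 7.2.3).
- m = those among the N with no response evaluation at all. Not in the documents; taken as 0, 5, 10 or 15.
- r = patients with recorded CR or CRi. Not in the documents; taken as 60.
- Interval method: 95% Clopper-Pearson (SAP 8.1.3).

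**Formulas**

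- Rate under the SAP: r/(N - m).
- Documented response among all N: r/N.
- Ratio of the two: N/(N - m). It exceeds 1 whenever m > 0 and does not depend on r.
- Upper bound on response among all N, if every unevaluated patient had in fact responded: (r + m)/N.

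**Results for N = 100, r = 60**

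| m | SAP rate (95% CI) | r/N (95% CI) | Ratio | Difference, points | Upper bound |
|---|---|---|---|---|---|
| 0 | 60/100 = 60.0% (49.7-69.7) | 60.0% (49.7-69.7) | 1.00 | 0 | 60% |
| 5 | 60/95 = 63.2% (52.6-72.8) | 60.0% (49.7-69.7) | 1.05 | 3.2 | 65% |
| 10 | 60/90 = 66.7% (55.9-76.3) | 60.0% (49.7-69.7) | 1.11 | 6.7 | 70% |
| 15 | 60/85 = 70.6% (59.7-80.0) | 60.0% (49.7-69.7) | 1.18 | 10.6 | 75% |

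The interval half-width is about 10 points in every row. At m = 5 the shift is about a third of that; at m = 15 it is about as large.

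The upper bound shows what is and is not known. If all m patients died before assessment, r/N is the response rate among the N. If some were merely lost or not assessed, the true rate lies between r/N and (r + m)/N, and the SAP rate lies inside that range.

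**Is the range for m plausible?** Take exponential survival with the protocol's median of 3 to 6 months and assume a first evaluation at 21 to 28 days. The proportion dead by day t is 1 - 2^(-t/median):

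- day 21: 7.7% (median 6 months) to 14.7% (median 3 months);
- day 28: 10.1% to 19.1%.

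This shows only that an m of 5 to 15 in 100 is not far-fetched; it does not estimate m. Survival on BESPONSA may be better than this background figure, the evaluation time is assumed, and some patients who die early will already have had refractory or progressive disease recorded.

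**Does anything else in the plan repair it?** Only in part. A patient with at least one evaluation stays in, through the last-cycle fallback or through best response, so later deaths and drop-outs are not lost. Table 1 (patient disposition) may show the set sizes, but its shell is not visible. No listed table gives a response rate on the safety analysis set.

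**The case against.** **Protocol-defined population.** The evaluated-only set is not a SAP departure, since protocol 7.7 defines it that way. This stands, and it is a reason to add a second rate rather than replace the first.

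**Removing only non-responders.** A reader might infer that the exclusion removes none but non-responders, so that the planned rate is simply wrong. The documents do not support that. It is certain for deaths before assessment. For patients who were lost, or whose evaluations were not done, response is unknown, and counting them as not effective is a conservative convention.

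**Importance.** A reader might also call these rates the study's main result. The SAP names no primary endpoint and has no formal hypothesis (SAP 4), and effectiveness appears only in the last of five objectives (SAP 2.2). No decision rule depends on either rate. This stands and lowers the severity. In a descriptive study, however, the estimate is the product, and these are the two overall effectiveness rates for which the SAP asks for an interval.

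**Size.** It rests on assumed inputs, and with m = 0 the problem disappears. Protocol 9.2 also provides for patients already exposed to the drug at consent, so early death counted from first dose need not apply to everyone enrolled. This stands too. The direction relative to documented response does not depend on these inputs.

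**Recoverable by the reader.** If Table 1 shows set sizes, r/N could be worked out by hand from Tables 32 and 36. That would give neither the reasons for non-evaluation nor the factor analyses.

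**Conclusion.** The point holds as a should-fix. The two CR/CRi rates describe evaluated patients and exceed the rate of documented response in the safety analysis set by the factor N/(N - m). With an assumed 100 treated and 60 responders, the excess is 3.2, 6.7 or 10.6 points for 5, 10 or 15 unevaluated patients, and zero if all are evaluated. The documents give neither m nor the response rate, so the real size is unknown.

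Measured against the true response rate, the upward bias is certain only as far as the unevaluated patients are early deaths. With losses of unknown response, the planned rate may be too high or too low. Nothing here shows that the evaluable-set rate is invalid for what it describes; the gap is that the plan offers no companion figure for treated patients.

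**What to change.** Keep the evaluable-set rates and add the following to the SAP:

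1. **SAP 8.2.3.2 and 8.2.3.5 (best overall response), Tables 32 and 36.** Report CR/CRi with a Clopper-Pearson interval on all safety-analysis-set patients, counting those with no response evaluation as not effective. Say that this is a conservative convention where response is unknown.
2. **Same tables.** Show the number never evaluated, split by the reason recorded under protocol 7.3.7 (death, loss to follow-up, other).
3. **Treated patients outside the safety set.** State how many were left out for safety follow-up failure (SAP 5.1, third exclusion). The safety-set denominator is itself not every treated patient, and the reader should see by how much.
4. **SAP 8.2.3.3 and 8.2.3.6.** Repeat the factor analyses on the same denominator as a sensitivity analysis.

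The cost is minor SAP wording, some table columns and one repeat of the factor models. No new data are needed, because the reasons are already collected. Since the protocol-defined set is kept, the change only adds to the plan in protocol 7.7. The added rate will be somewhat lower than the evaluable-set rate if any patient went unevaluated. The rule should be fixed before the final re-examination analysis.

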5.3 SPECIAL POPULATION SET

Patients who are included in safety analysis set or effectiveness analysis set will be categorized into the following special population set.

1. Elderly (≥ 65 years)
2. Hepatic disorder
3. Renal disorder

5.4 NON-SAFETY POPULATION SET

If patients excluded from safety analysis are collected, such as in off-label use cases, these patients are classified as non-safety population set and any adverse events occurring during the PMS period shall be additionally checked or separately analyzed as the per needed.

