7.2.4. Dosage and administration

The use and dosage recommendations for BESPONSA® should take place on the basis of the approved LPD. If subjects have been administered BESPONSA® off label, they should be excluded from the safety analysis set and analyzed separately.

Refer to the most updated LPD for the detailed information on prescription.

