5.1 SAFETY ANALYSIS SET

The safety analysis set includes patients who have been administered BESONSA® at least once and evaluated with safety-related endpoints at least once.

Patients meeting any of the following criteria will be excluded in the safety analysis set.

1. Patients who received BESONSA® prior to site initiating contract date
2. Patients who didn't receive BESONSA®
3. Safety follow-up failure: Patients without documented evidence for whom adverse event status was evaluated(Patients with "Whether AE status was evaluated" checked as No in the eCRF OR no answer is provided to question "Whether a patient has AE" in the eCRF)
4. Patients who violated inclusion/exclusion criteria
5. Patients who violated usage
6. Patients who have enrolled twice or more (i.e. if a patient has been assigned to two or more subject ID or CRFs, only one record clarified by site will be used for analysis and the others will be excluded)

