8.2.4 Non-safety population Analyses

The following adverse events from non-safety population shall be summarized by SOC and PT using the number of subjects(n), percentage(%), number of events and 95% confidence interval of percentage.

- AE·ADR
- Serious AE·ADR
- Unexpected AE·ADR
- Unexpected serious AE·ADR

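### The non-safety set, read literally, pools off-label patients with never-dosed and AE-unassessed patients, so its AE percentages can be diluted and no planned table isolates off-label use

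*SAP*

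**What the plan says.** Protocol 7.2.4 says of subjects given the drug off label that "they should be excluded from the safety analysis set and analyzed separately".

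SAP 5.1 lists six reasons for exclusion from the safety analysis set: dosing before the site contract date, no dosing ("Patients who didn't receive BESONSA"), AE status not evaluated ("Safety follow-up failure: Patients without documented evidence for whom adverse event status was evaluated"), violation of the inclusion or exclusion criteria, violation of usage ("Patients who violated usage"), and duplicate enrolment ("Patients who have enrolled twice or more").

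SAP 5.4 defines the non-safety set by exclusion: "If patients excluded from safety analysis are collected, such as in off-label use cases, these patients are classified as non-safety population set". It continues that "any adverse events occurring during the PMS period shall be additionally checked or separately analyzed as the per needed".

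SAP 8.2.4 drops the conditional wording: "The following adverse events from non-safety population shall be summarized by SOC and PT using the number of subjects(n), percentage", together with event counts and the 95% confidence interval of the percentage. The list of tables reserves Tables 40 to 43 for this. Under SAP 8.1.3 the intervals are Clopper-Pearson unless otherwise specified.

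**The concern.** A proportion with an exact binomial interval needs a denominator of people in whom the event could have been observed. Two of the six exclusion groups fail that test. A never-dosed patient cannot have an ADR, and under Protocol 9.2 safety reporting starts at first dose, or at the data privacy statement if the patient is already exposed. A patient whose AE status was not evaluated has an unknown outcome, not a negative one. SAP 5.1 removes both groups from the main safety set, but SAP 5.4 and 8.2.4 then place them in the denominator of another AE percentage.

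The second issue is what the tables describe. Off-label patients are kept apart from the safety set, but they are mixed with every other kind of excluded patient. A reader of Tables 40 to 43 could take the result as the off-label AE proportion when it is a proportion over a mixed group.

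**Working it through.** **No figure to reproduce.** The documents give no size, composition or AE rate for the non-safety set. The check is therefore a reading of the sections together, then a general formula, then illustrations on assumed counts.

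**Step 1: who is in the set.** Membership under SAP 5.4 is exclusion from the safety analysis.

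| Exclusion in SAP 5.1 | Dosed? | AE outcome known? |
|---|---|---|
| 1. Dosed before site contract | Yes | Can be |
| 2. Never dosed | No | No on-drug period; ADR impossible |
| 3. AE status not evaluated | Can be | No |
| 4. Inclusion/exclusion violation | Can be | Can be |
| 5. Usage violation (the off-label route) | Yes | Can be |
| 6. Duplicate enrolment | One record kept for analysis | Surplus records excluded |

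Neither SAP 5.4 nor 8.2.4 removes groups 2 and 3 or separates group 5 from the rest.

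**Step 2: does the missing-data rule repair this?** SAP 7 excludes missing values from the corresponding analyses. That could remove patients whose AE question is blank. It does not clearly remove those recorded as No on whether AE status was evaluated, because that is an answer. It does nothing about never-dosed patients.

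**Step 3: size of the effect.** Let m be the treated and assessed patients, x those with an AE, and k the untreated or unassessed patients with no AE recorded.

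- Proportion among evaluable patients: x/m
- Proportion as written: x/(m+k) = (x/m) × m/(m+k)

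If 10%, 20%, 30% or 50% of the set is untreated or unassessed, the factor is 0.9, 0.8, 0.7 or 0.5.

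**Step 4: illustrations (all counts assumed), Clopper-Pearson 95% intervals.**

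| m | x | Evaluable only | k | As written |
|---|---|---|---|---|
| 4 | 2 | 50.0% (6.8 to 93.2) | 3 | 2/7 = 28.6% (3.7 to 71.0) |
| 5 | 4 | 80.0% (28.4 to 99.5) | 5 | 4/10 = 40.0% (12.2 to 73.8) |
| 10 | 8 | 80.0% (44.4 to 97.5) | 2 | 8/12 = 66.7% (34.9 to 90.1) |
| 10 | 8 | 80.0% (44.4 to 97.5) | 5 | 8/15 = 53.3% (26.6 to 78.7) |
| 10 | 8 | 80.0% (44.4 to 97.5) | 10 | 8/20 = 40.0% (19.1 to 64.0) |
| 20 | 16 | 80.0% (56.3 to 94.3) | 5 | 16/25 = 64.0% (42.5 to 82.0) |

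In the first row, 0.50 × 4/7 = 0.286, as the formula gives.

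**Step 5: can the off-label result be recovered elsewhere?** Tables 40 to 43 are the only listed AE tables for the non-safety set. They are divided by event type (all, serious, unexpected, unexpected serious), not by exclusion reason. No listed table isolates usage violators.

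**The case against.** **The effect is conditional, and other text limits it.** SAP 5.4 opens with an if and makes separate analysis a matter of need. Protocol 7.3.8 assesses safety in patients who had at least one dose and completed safety follow-up. Protocol 7.3.1 takes cases that fail the privacy or enrolment confirmation out of the study altogether. Never-dosed patients may therefore be few or none. This stands: dilution occurs only if such patients are collected. It does not remove the problem, because SAP 5.1 expressly provides for both groups and SAP 8.2.4 is unconditional.

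**The protocol does not ask for an off-label AE rate.** It asks for separate analysis, and separation from the safety set is one reasonable reading. That is fair as far as it goes. Even so, a mixed group does not show the off-label patients' own experience.

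**The study is descriptive.** SAP 4 states no formal hypothesis. The main safety and effectiveness tables are unaffected, and SAP 8.2.4 also reports subject and event counts, which do not depend on the denominator. The illustrative intervals overlap widely. All of this stands and limits the importance of the point.

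**Duplicates.** A reader might infer that surplus records of duplicated patients enter the set, so that the same AEs are counted in both Table 14 and Table 40. The documents do not support this. Item 6 of SAP 5.1 keeps one record for analysis and excludes the others, and SAP 5.4 classifies patients, not records. Nor can duplicates be assumed to dilute: if two surplus records with AEs did enter, 8/10 = 80.0% would rise to 10/12 = 83.3%.

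**Conclusion.** The point holds as a conditional one. As written, SAP 5.1, 5.4 and 8.2.4 together require AE and ADR percentages, with exact intervals, on a set that admits patients who could not have the event or were not checked for it. If such patients are collected, the percentage is biased downward by m/(m+k), assuming they carry no recorded AEs and are not dropped under SAP 7. The actual size cannot be derived from the documents, and every count above is an assumption.

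The lack of an off-label breakdown does not depend on counts: no planned table gives it. The consequence is confined to four supplementary descriptive tables. It is worth correcting because the correction is cheap and would give Protocol 7.2.4 a readable off-label analysis.

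**What to change.** Amend SAP 5.4 and 8.2.4 as follows:

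- Calculate the percentages and confidence intervals in Tables 40 to 43 only on unique patients with at least one dose and AE status assessed.
- Within those tables, show off-label (usage-violating) patients as their own group, apart from patients excluded for other reasons.
- Report never-dosed and AE-unassessed patients by reason in Table 1 (patient disposition), and list any AEs recorded for them so that nothing is lost.
- State that surplus duplicate records enter no analysis set.
- Align the as-needed wording of 5.4 with the unconditional wording of 8.2.4.

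The cost is SAP text and table shells. SAP 5.1 already defines the exclusion reasons, so no new data collection should be needed. The downside is smaller denominators and generally wider intervals.

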6. ENDPOINTS AND COVARIATES

6.1 SAFETY ENDPOINTS

- Adverse event, serious adverse event, adverse drug reaction or unexpected adverse event

6.2 EFFECTIVENESS ENDPOINTS

- Response evaluations at each cycle and the final evaluation:
CR | CRI | Refractory disease | Progressive disease | Relapsed disease
- Last effectiveness†:
†: Based on 'final effectiveness evaluation' or 'last cycle response evaluation(if the final evaluation is missing)'
Effective (CR, CRI) |
Ineffective (Refractory disease, Progressive disease, Relapsed disease)

6.3 OTHER ENDPOINTS

Not Applicable

6.4 COVARIATES

The demographics and baseline characteristics listed in section 8.2.1 could be considered as covariates to identify the factors that may affect safety or effectiveness.

7. HANDLING OF MISSING VALUES

There are no plans for imputation of missing values for variables; all missing values will be excluded from corresponding analyses. The impact of missing data will be evaluated as appropriate.

However, if the causality of the study drug on adverse event is missing, it will be considered 'related' and classified as adverse drug reaction(ADR).

8. STATISTICAL METHODOLOGY AND STATISTICAL ANALYSES

8.1 STATISTICAL METHODS

The analysis of this study is primarily descriptive. Data shall be presented by following unless otherwise specified.

8.1.1 Analysis for Continuous Data

The continuous variables will be summarized using the following parameters.

- Number of subjects(n)
- Mean±Standard deviation (Mean±SD)
- Median
- Minimum and Maximum (Min, Max)

8.1.2 Analysis for Categorical Data

The categorical data will be summarized using the following parameters.

- Number of subjects(n)
- Percentage (%)
- 95% Confidence Interval (If applicable)
- Events (Events, If applicable)

